- 11. Serum pregnancy testing will be conducted at Screening (within ≤ 7 days of C1D1). Serum or urine pregnancy tests thereafter will be done on Day 1 of every cycle for all premenopausal and perimenopausal female subjects of childbearing potential, including EOT and the Safety Follow-up Visit.
- 12. Plasma samples for PK analysis of ZN-c5 (having been administered without food [at least 1 hour before and 2 hours after a meal]) and of palbociclib (having been administered with food) will be collected relative to ingestion of each drug as per Table 6 and Table 7. Regarding the PK sampling for ZN-c5 if administered twice daily (BID), a sample at 12 hours post morning dose and immediately preceding the second daily dose may also be collected (optional). Note: If the optional, On-Treatment tumor biopsy is performed, an additional PK sample should be collected at that time.
- 13. Whole blood, serum and/or plasma will be collected for exploratory biomarkers at C1D1, C2D1, and at time of disease progression.
- 14. Tumor biopsy: At baseline, *de novo* biopsy of any amenable site of disease (at investigator's discretion). Additional tumor biopsy at C2D1 or any time beyond may also be obtained. The on-treatment biopsy should be obtained 2 4 hours after the subject has taken the ZN-c5 dose that day. Subjects will also have the option to undergo a biopsy of a lesion at the time of disease progression. Samples will be collected, labelled, stored and shipped as detailed in the laboratory manual. Any residual tumor remaining after analysis may be used for exploratory research into factors that may influence development of breast cancer and/or response to ZN-c5. All tumor biopsies are optional for all subjects participating during the study. Biopsies must not be taken from target lesions used to assess anti-tumor efficacy, if possible. If sufficient tumor material is available, part of the tumor biopsy at C2D1 will be used for determination of ZN-c5 tissue concentration. If a biopsy is obtained on C2D1 or beyond, a plasma PK sample should also be collected, as close as possible, within 2 hours prior to the biopsy.
- 15. A blood sample for the assessment of ESR1 mutations will be drawn at C1D1, C2D1, and at time of progression.

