- 16. Tumor evaluation by CT/MRI or applicable scan will be performed during Screening (within 28 days of Cycle 1 Day 1) and every 8 weeks (± 7 days) after C1D1 for the first 24 weeks. After 24 weeks, scans may be performed every 12 weeks (± 7 days). The same radiographic procedure used to define measurable lesions must be used throughout the study for each subject. Applicable scans to be done at EOT visit if not done within the previous 4 weeks.
- 17. Plasma samples for 4β -hydroxycholesterol and cholesterol will be collected pre-dose on C1D1, C1D15, and pre-dose on Day 1 of Cycles 2-4 of the Monotherapy Dose Escalation and Expansion.
- 18. A FES-PET scan (optional) should be conducted at Screening and at least after 1 month of treatment (preferably within the first 2 months, in Cycle 2).
- 19. Beginning on C1D1, subjects will take ZN-c5 once daily (alternatively, this total daily dose may be divided by 2 and administered BID [every 12 hours]). ZN-c5 dosing and administration as per assigned cohort (see Section 6.1.2.1).
- 20. In Phase 1, beginning on C1D1, subjects in the combination treatment cohorts will take palbociclib at the label indicated dose of 125 mg orally once daily (2 hours after the ZN-c5 dose was taken) for 21 consecutive days followed by 7 days off treatment (1 cycle of treatment = 28 days) (see Section 6.1.2.2). In Phase 2, subjects in the combination treatment cohorts will take palbociclib at the label indicated dose of 125 mg orally once daily (at the same time the ZN-c5 dose is taken) for

- 21 consecutive days followed by 7 days off treatment (1 cycle of treatment = 28 days).21. Disease Assessment Follow-up Visit: Subjects without progression of disease (PD) at the time of study drug discontinuation will continue to undergo disease evaluations every 12 weeks \pm 7 days until confirmation of PD, initiation of the first subsequent cancer therapy, withdrawal of consent, death, loss to follow-up, or until the study is terminated. Once a subject has confirmation of PD or has initiated subsequent cancer therapy, whichever occurs first, disease follow-up will discontinue.
- 22. Long-term Follow-up (LTFU) Subjects will be contacted every 3 months (phone or medical records) for survival status and collection of subsequent breast cancer treatments.

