6.1.2.2 DOSING AND ADMINISTRATION OF PALBOCICLIB

Palbociclib (IBRANCE®, Pfizer Inc.) at a dose of 125 mg should be taken orally once daily for 21 consecutive days, followed by 7 days off treatment to comprise a complete cycle of 28 days, per the most recent local or US Full Prescribing Information for palbociclib. Subjects should take palbociclib at approximately 24-hour intervals at approximately the same time each day.

On days that PK samples are drawn, palbociclib should be taken with food 2 hours after the ZN-c5 dose.

If a subject vomits or misses a dose, an additional dose should not be taken. The next prescribed dose should be taken at the usual time. Palbociclib should be swallowed whole (do not chew, crush, or open them prior to swallowing). Palbociclib should not be ingested if the medication is broken, cracked, or otherwise not intact.

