8.2.2 PHARMACOKINETIC, PHARMACODYNAMIC, & CORRELATIVE SAMPLES

8.2.2.1 PHARMACOKINETIC SAMPLES

Details of sample preparation and procedures for transfer of samples to the central laboratory are provided in the Laboratory Manual.

Plasma samples for ZN-c5 (and its potential metabolites as applicable) (± palbociclib) will be collected as described in Table 5.

b Includes direct bilirubin

Table 5: Pharmacokinetic Sampling per Study Component

Study Component	N subjects and type of PK	PK Time Points
Monotherapy Dose Escalation	therapy Dose Escalation Full ZN-c5 PK in all subjects	
Monotherapy Expansion – at each dose level assessed	Full ZN-c5 PK in approximately 6 – 12 subjects in total, subjects from the Monotherapy Dose Escalation treated at the same dose level and with evaluable PK data included	Table 6 (Monotherapy)
	Abbreviated ZN-c5 PK schedule for the remaining subjects (optional)	Table 7
Monotherapy Phase 2	Abbreviated ZN-c5 PK schedule in all subjects (optional)	Table 7
Combination Dose Escalation	Full ZN-c5 + palbociclib PK in all subjects	Table 6 (Combination Therapy)
Combination Phase 2 – Stage 1 – at each dose level assessed	Full ZN-c5 + palbociclib PK in approximately 6 – 12 subjects in total, subjects from the Combination Dose Escalation treated at the same dose level and with evaluable PK data included	Table 6 (Combination Therapy)
	Abbreviated ZN-c5 + palbociclib PK schedule for the remaining subjects (optional)	Table 7
Combination Phase 2 – Stage 2	Abbreviated ZN-c5 + palbociclib PK schedule in all subjects (optional) Table 7	

The decision to switch from a full PK schedule to an abbreviated PK schedule (population PK) will depend on the variability of the ZN-c5 PK parameters observed in the subjects with full PK. If required, more subjects in the Monotherapy Phase 2 or in the Combination Phase 2 (Stage 2) will continue to be assessed with full PK.

In the combination cohorts, on PK days, palbociclib should be taken with food 2 hours after the ZN-c5 dose.

Table 6: Full Pharmacokinetic Sampling Time Points

Day on Study	Time (hr)	Monotherapy	Combination Therapy	
		ZN-c5	ZN-c5	Palbociclib
Cycle 1 Day 1 and 15	T=0	PK (pre-dose, within 0.5 hrs)	PK (pre-dose, within 0.5 hrs)	NA
		Dose (fasted)	Dose (fasted)	NA
	0.5	PK	PK	NA
	1	PK	PK	NA
	2	PK	PK (prior to Palbociclib dosing)	PK (pre-dose, within 0.5 hrs) Dose (with food)
	2.5	NA	NA	PK (0.5-hr)
	3	NA NA	NA NA	PK (0.3-111)
	4	PK	PK	PK (1-111)
	6	PK	PK	PK (4-hr)
	8	PK	PK	PK (6-hr)

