	10	NA	NA	PK (8-hr)
Cycle 1	24	PK	PK	NA
Day 2 and 16	26	NA	NA	PK (24-hr)
Cycle 1 Day 8		PK (pre-dose, within 0.5 hrs)	PK (pre-dose, within 0.5 hrs)	РК
Cycle 2 Day 1		PK (pre-dose, within 0.5 hrs)	PK (pre-dose, within 0.5 hrs)	NA
Cycle 3 Day 1		PK (pre-dose, within 0.5 hrs)	PK (pre-dose, within 0.5 hrs)	NA
Cycle 4 Day 1		PK (pre-dose, within 0.5 hrs)	PK (pre-dose, within 0.5 hrs)	NA
NA= not applic	able	,	,	

In case the dosing schedule is changed to BID dosing, an additional PK time point at 12 hours post ZN-c5 dosing will be drawn (optional).

Table 7: Abbreviated Pharmacokinetic Sampling Time Points

Day of Study	Collection Time Points (and Allowable Windows)	ZN-c5	Palbociclib*
Cycle 1 Day	Pre-dose (within 0.5 hour prior to ZN-c5 administration)	Х	Х
15	2-hours (± 10 min) post ZN-c5 administration	Х	Х
	4-hours (± 1 hour) post ZN-c5 administration	Χ	Х
*in the combination parts of the study			

All efforts will be made to obtain the PK samples at the exact nominal time relative to dosing, however, samples obtained within 10% of nominal time from dosing are acceptable for up to and including the

12-hour time points. The 24-hour time points should be drawn within \pm 1 hour. A protocol deviation only applies if a PK time point is missed.

If the optional On-Treatment tumor biopsy is performed, an additional PK sample should be collected at that time, regardless if tissue was obtained for ZN-c5 tissue concentration.

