6.7.2 Plasma Concentrations

The plasma concentrations of ZN-c5, palbociclib, and/or metabolites will be summarized using nominal sampling time by visit, cohort, dosing regimen (i.e. QD or BID), and analyte using descriptive statistics. A listing by subject of plasma concentrations and/or tumor concentrations of ZN-c5 (if available), sample collection times, and derived sampling time deviations will be provided.

Nominal sampling time points relative to dosing will be used for mean plots of concentration-time data. Actual sampling times will be used for individual concentration-time plots, including all recorded concentrations regardless of timing. BQL concentration values will be set to 0 for predose of Day 1, and set to a value equal to the LLOQ for all other time points for calculation of summary statistics and display. Summary statistics for concentration-time data will include n, mean, SD, arithmetic coefficient of variation (%), minimum, median, maximum, geometric mean, and geometric coefficient of variation (%).

The arithmetic and geometric means of plasma concentrations of ZN-c5, palbociclib, and metabolites, will be presented graphically on both linear and semi-logarithmic scales by visit, cohort, dosing regimen, and analyte. For individual profiles, figures will be presented for each subject with concentration-time profiles on both linear and semi-logarithmic scales. Concentration values of 0 will not be plotted in the semi-logarithmic plots. The following figures will be produced:

- Individual concentration versus actual time – linear scale (overlaid for each cohort)
- Individual concentration versus actual time – semi-log scale (overlaid for each cohort)
- Arithmetic Mean concentration versus nominal time – linear scale (overlaid for all cohorts)
- Arithmetic Mean concentration versus nominal time – semi-log scale (overlaid for all cohorts)
- Geometric Mean concentration versus nominal time – linear scale (overlaid for all cohorts)
- Geometric Mean concentration versus nominal time – semi-log scale (overlaid for all cohorts)

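### Combination Phase 2: the schedule has palbociclib taken together with ZN-c5 but the PK-day text has it 2 hours later, so the optional Table 7 palbociclib sample at 2 hours can be a trough or a post-dose level

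*Protocol*

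**What the plan says.** - **Schedule footnote 20** (Protocol 1.3; SAP 3.7). In Phase 1, palbociclib follows ZN-c5 by 2 hours, with a reference to Section 6.1.2.2. In Phase 2 it is taken "at the same time the ZN-c5 dose is taken" on each of the 21 dosing days. The Phase 2 sentence has no cross-reference and no PK-day exception.
- **Protocol 6.1.2.2.** "On days that PK samples are drawn, palbociclib should be taken with food 2 hours after the ZN-c5 dose". No phase is named.
- **Protocol 8.2.2.1.** "In the combination cohorts, on PK days, palbociclib should be taken with food 2 hours after the ZN-c5 dose". Again no phase is named.
- **Schedule footnote 12.** On sampling days ZN-c5 is taken without food, and samples "of palbociclib (having been administered with food) will be collected relative to ingestion of each drug".
- **Protocol 6.1.2.1.** In Phase 2, ZN-c5 may be taken with or without food.
- **Table 5.** In Combination Phase 2 the abbreviated schedule (Table 7) is optional. It applies to the Stage 1 subjects who are not on full sampling and to all Stage 2 subjects. About 6 to 12 subjects per dose level in Stage 1, counting eligible escalation subjects, follow Table 6.
- **Table 7.** Three draws on Cycle 1 Day 15, each marked for both drugs: pre-dose, "2-hours (± 10 min) post ZN-c5 administration", and 4 hours ± 1 hour. All three are referenced to ZN-c5.
- **Table 6.** The palbociclib dose is written in at 2 hours, and the ZN-c5 draw at that point is marked as coming before it.
- **SAP 6.7.2.** Concentrations "will be summarized using nominal sampling time by visit, cohort, dosing regimen" and analyte. Protocol 9.4.10.1 also summarises by nominal time.

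**The concern.** Cycle 1 Day 15 is both a palbociclib dosing day and the Table 7 sampling day, so in Combination Phase 2 both timing rules apply to it and they give different answers. Footnote 12 adds to the conflict: a fasted ZN-c5 dose and a fed palbociclib dose cannot be taken together.

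A site could follow either text in good faith. Under 8.2.2.1 only a missed PK time point counts as a deviation, so deviation records would not show which rule was used. Table 7 carries no palbociclib-relative time, so samples drawn at different points of the palbociclib profile would share a nominal label and be averaged. Palbociclib PK in the presence of ZN-c5 is a secondary objective, and these summaries feed its Phase 2 part.

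**Working it through.** No sample size or error rate is involved, and the plan states no figure to reproduce. The check is timing arithmetic.

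**Inputs.** Table 7 draw times relative to ZN-c5: −0.5 to 0 h; 2 h ± 10 min (10/60 = 0.17 h); 4 h ± 1 h. Palbociclib offset from ZN-c5 on the day: 0 h (footnote 20) or 2 h (6.1.2.2 and 8.2.2.1). Assumption: ZN-c5 once daily at 24-hour intervals.

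**Formulas.**
- Time since that day's palbociclib dose = draw time − offset.
- Time since the previous day's dose = draw time + 24 − previous day's offset.

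**Time since that day's palbociclib dose, nominal (range):**

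| Table 7 draw | Footnote 20, offset 0 h | PK-day text, offset 2 h |
|---|---|---|
| Pre-dose | 0 h (−0.5 to 0) | −2 h (−2.5 to −2) |
| 2 hours | 2 h (1.83 to 2.17) | 0 h (−0.17 to 0.17) |
| 4 hours | 4 h (3 to 5) | 2 h (1 to 3) |

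**Time since the previous dose, 2-hour draw under the PK-day text.** If the day before was same-time dosing: 2 + 24 − 0 = 26 h. If the day before also had the gap: 2 + 24 − 2 = 24 h.

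All three draws shift by 2 h, but only the 2-hour draw changes kind, from post-dose level to trough. The pre-dose draw precedes the day's palbociclib dose under both rules, and the 4-hour draw follows it under both, with ranges that meet at 3 h. Under the PK-day text the ± 10 minute window straddles the dose, and Table 7 does not say which comes first.

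**Table 6 in Phase 2.** The same formula applies if a subject on full sampling followed footnote 20. The palbociclib draw labelled pre-dose, at 2 h on the ZN-c5 clock, would be 2 − 0 = 2 h post-dose, and no palbociclib draw is scheduled at time 0.

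**Which analyses are reached.** SAP 6.7.1 uses actual times relative to each drug for noncompartmental analysis, except that Day 1 and Day 15 pre-dose points are set to 0. Apart from that exception, the exposed outputs are the nominal-time summaries and mean plots. SAP 6.5.6 reproduces only the full sampling table, so the SAP gives no palbociclib label for the Table 7 draws.

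**The case against.** The best defence is that a specific rule overrides a general one. Sections 6.1.2.2 and 8.2.2.1, Table 6 and footnote 12 all describe PK days and agree with each other, and footnote 20 is the everyday instruction. On that reading, PK days follow the 2-hour gap, and the single 26-hour interval is compatible with a protocol that asks only for approximately 24-hour intervals. This is a reasonable reading, but nothing states it. Footnote 20 covers every Phase 2 dosing day and refers to 6.1.2.2 only for Phase 1. Even on this reading, Table 7 leaves the order of draw and dose at 2 hours open.

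The defence is stronger on consequence, and most of it stands. Diaries record dosing times, and SAP 6.7.2 lists collection times and plots individual profiles on actual time. Table 7 sampling is optional. All Combination Dose Escalation subjects (about 40) have full palbociclib sampling, and there footnote 20 and 6.1.2.2 agree.

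Two stronger readings are tempting, and the documents do not support them:
- **That two of the three abbreviated samples confuse trough with absorption.** Only the 2-hour draw does. The documents give no concentrations, so the size of the difference cannot be stated.
- **That the secondary objective becomes unreadable.** Its endpoint is PK parameters, which rest mainly on full profiles. Three draws could not supply most of them in any case: SAP 6.7.3 requires at least three terminal-phase points, excluding the maximum, to estimate the terminal slope.

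**Conclusion.** The contradiction holds as an internal inconsistency between stated rules, of minor severity. It reaches the nominal-time summaries and mean plots of Combination Phase 2 palbociclib samples. In the Table 7 2-hour cell, a level about 2 h post-dose could be pooled with one 24 to 26 h after the previous dose; in the 4-hour cell, levels about 4 h and about 2 h post-dose could be pooled. Noncompartmental analysis is touched only through pre-dose points set to 0, and only if a Table 6 subject followed footnote 20. Combination Dose Escalation results are unaffected.

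This assumes that Combination Phase 2 is run, which SAP 5.2 treats as conditional and the documents do not settle. It also assumes that some subjects give the optional samples and that sites do not all follow the same passage. If every site followed one rule, nothing would be mixed, but the label would still not say what the sample represents. No view is taken on which dosing time is right.

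**What to change.** - Reconcile footnotes 12 and 20, Sections 6.1.2.2 and 8.2.2.1, and Tables 6 and 7 into one statement of palbociclib timing and food conditions on Phase 2 PK days. Carry it into the SAP copy of the schedule. The choice of rule is the sponsor's.
- In Table 7 and SAP 6.7.2, give palbociclib nominal times relative to the palbociclib dose, and state whether the 2-hour draw comes before or after that dose.
- For samples already taken, assign the palbociclib time label from the recorded dosing and collection times before summarising.

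The cost is a protocol clarification and a change of SAP labels. No extra samples or subjects are needed.

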1.3 SCHEDULE OF ACTIVITIES

Table 1: Study Procedures Table

Study Phase	Screening		(28	Cycle 1	cle)			'ycles ≥ 2 -day cycle)	ЕОТ	30-day Safety Follow- up	Disease Assess ment Follow- up ²¹ (every 12 weeks)	Survival Follow- up ²² (every 12 weeks)
Cycle Day	Day -28	Day 1	Day 2	Day 8	Day 15	Day 16	Day 1	[Day 15* Cycle 2 Combination only]				
Window (days)	-28 to -1			± 1	± 2		[± 4 ²³]	[± 2]	± 7	± 7	± 7	± 14
Informed Consent	Х											
Medical and Medication History ¹	х											
Physical Examination ²	х	х		х	х		х	[X]	Х	Х		
ECOG Performance Status	Х	х					х	[X]	Х	Х		
Vital Signs ³	Х	Х		Х	Х		Х	[X]	Х	Х		
Triplicate 12- lead ECG ⁴	Х	х	[X]		Х	[X]	[X]		Х			
Adverse events/ Concomitant medications ⁵	[X]	х	[X]	х	х	[X]	х	[X]	х	х		
Enrollment	Х											
Hematology	X ⁷	Х		Х	Х		Х	[X]	Х	Х		
Chemistry	X ⁷	Х		Х	Х		Х	[X]	Х	Х		
Coagulation ⁸	X ⁷								Х			
Full Lipid Panel ⁹		[X]					[X]					
Urinalysis ¹⁰	X ⁷								Х			
Pregnancy Test ¹¹	Х	Х					х		Х	Х		
PK ¹²		[X]	[X]	[X]	[X]	[X]	[X]					

Study Phase	Screening		(28	Cycle 1 3-day cyc				'ycles ≥ 2 -day cycle)	ЕОТ	30-day Safety Follow- up	Disease Assess ment Follow- up ²¹ (every 12 weeks)	Survival Follow- up ²² (every 12 weeks)
Cycle Day	Day -28	Day 1	Day 2	Day 8	Day 15	Day 16	Day 1	[Day 15* Cycle 2 Combination only]				
Window (days)	-28 to -1			± 1	± 2		[± 4 ²³]	[± 2]	± 7	± 7	± 7	± 14
ZN-c5 pharmaco- dynamic and exploratory biomarkers in blood ¹³		х					х		[X]		[X]	
Tumor Biopsy ¹⁴	[X]						[X]		[X]		[X]	
ESR1 Mutation ¹⁵		х					х		[X]		[X]	
CT/MRI ¹⁶	Х						Х		Х		[X]	
4β- hydroxycholest erol / cholesterol ¹⁷		х			х		х					
FES-PET ¹⁸	[X]						[X]					
ZN-c5 oral dosing ¹⁹						Х						
Palbociclib oral dosing (Combo only) ²⁰			[X]									
Subject Dosing Diary Accountability and/or Dispensing ⁶		х					х		Х			
LTFU ²²												[X]

Notes: X = Required; [X] = Only applicable as per footnote as indicated by the Assessment

Cycle 1 Day 1 safety lab samples, physical examination, ECOG status and pregnancy test may be assessed up to 3 days prior to the Day 1 visit. On subsequent visits throughout the study, these procedures/assessments are allowed to be performed within 1 day prior to the planned visit.

Cycle 1 Days 2 and 16 are only required for subjects participating in the Phase 1 parts of the protocol.

*Cycle 2 Day 15 visit – only for subjects participating in Combination Therapy (Combination Dose Escalation and Phase 2)

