- 23. In the Combination Dose Escalation and Combination Phase 2 with palbociclib, the window for the Day 1 visit for subsequent cycles is only + 4 days, since there must always be at least a full 7-day off treatment recovery period for palbociclib before starting the next 21-day dosing cycle.

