8.4 DOSE-LIMITING TOXICITIES AND TOXICITY MANAGEMENT

8.4.1 DEFINITION OF DOSE-LIMITING TOXICITY MONOTHERAPY DOSE ESCALATION

A dose-limiting toxicity (DLT) is a toxicity as defined below, excluding toxicities clearly related to disease progression or intercurrent illness, which occurs during the DLT evaluation period (Cycle 1) in each cohort:

- Grade ≥ 3 hematologic toxicity present for more than 7 days
- Grade ≥ 3 neutropenia (ANC < 1000/mm³) with fever (a single temperature of > 38.3°C or a sustained temperature of ≥ 38°C for more than one hour)
- Grade 3 thrombocytopenia with bleeding
- Grade ≥ 3 or higher non-hematologic toxicity, except:
 - Grade 3 nausea or emesis with maximum duration of 48 hours on adequate medical therapy
 - Grade 3 diarrhea which persists for < 72 hours in the absence of maximal medical therapy
- Grade ≥ 2 non-hematologic treatment-emergent adverse event (TEAE) that in the opinion of the
 investigator is of potential clinical significance such that further dose escalation would expose
 subjects to unacceptable risk
- Treatment interruption of ≥ 4 days due to drug-related toxicity
- Liver enzyme and bilirubin abnormalities meeting Hy's Law criteria (See Section 10.4.7)
- Any death not clearly due to the underlying disease or extraneous cause

For certain toxicities, such as laboratory assessments without a clear clinical correlate, a discussion between the investigator and Medical Monitor may take place to determine if this adverse event (AE) should be assessed as a DLT necessitating dose reduction. In addition, any toxicity which occurs during the DLT evaluation period meeting the protocol-defined stopping criteria (Section 7.1) will be considered a DLT.

During the DLT evaluation period (Cycle 1), subjects not completing at least 24 days of scheduled daily dosing of ZN-c5 for reasons other than drug-related toxicity (e.g., withdrawal of consent, rapid disease progression, etc.) may be replaced based on the discretion of the Safety Review Committee.

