8.4.2 DEFINITION OF DOSE-LIMITING TOXICITY – COMBINATION DOSE ESCALATION

A DLT is a toxicity as defined below, excluding toxicities clearly related to disease progression or intercurrent illness, which occurs during the DLT evaluation period (Cycle 1) in each cohort:

- Hematologic:
 - o Grade 4 neutropenia
 - Febrile neutropenia (defined as neutropenia Grade ≥ 3 [ANC < 1000 cells/mm³] and a body temperature ≥ 38.5°C) requiring antibiotic or antifungal treatment
 - o Any Grade 4 thrombocytopenia (< 25,000/mm³ or <25.0 x 109/L)
- Nonhematologic:
 - o Grade ≥ 3 toxicities despite adequate treatment (e.g., nausea, vomiting, diarrhea)
- Other:
 - o Any palbociclib treatment delay of greater than 7 days to start Cycle 2

Subjects who do not receive at least 24/28 doses of ZN-c5 and/or at least 85% of palbociclib doses in Cycle 1 for reasons other than DLT will be replaced.

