9.3 POPULATIONS FOR ANALYSES

Full Analysis Set (FAS)

The FAS includes all subjects who receive ≥ 1 dose of study drug. This analysis set will be used for subject characteristics and efficacy endpoints.

Safety Analysis Set

The Safety Analysis Set for this study will be the same as FAS as this study is not randomized. This analysis set will be used for safety endpoints, study treatment administration and post-study therapy.

DLT-Evaluable Analysis Set

The DLT-Evaluable Analysis Set includes all subjects in the Safety Analysis Set who take ≥ 24/28 scheduled Cycle 1 doses of ZN-c5 and/or the cumulative dose of palbociclib was ≥ 85% in Cycle 1 (or less, if for reasons due to DLTs) and underwent all treatment and safety procedures through Day 28 or experienced a DLT prior to Day 28. Determination of the MTD will be in the DLT-Evaluable Analysis Set.

Pharmacodynamic and Pharmacokinetic Analysis Sets

The Pharmacodynamic and PK Analysis Sets consist of all subjects in the FAS who have the necessary baseline and on-study measurements to provide interpretable results for the specific parameters of interest.

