10.1.6 SAFETY OVERSIGHT

In the Phase 1 Monotherapy and Combination Dose Escalation, the safety and tolerability of each dose level will be assessed by a Safety Review Committee after all subjects in the cohort have been followed for at least 28 days after the first dose of ZN-c5. The Safety Review Committee will consist of the Study Team Physician/Medical monitor (or delegate) who will serve as chair of the committee and the Principal Investigator or delegate from each investigational site (or delegate). Others may be invited on an ad hoc basis, including (but not limited to) project team manager, preclinical team lead, study statistician, or others. Other internal or external experts may be consulted as needed. Frequent safety assessments will be conducted throughout Phase 1 (Monotherapy Expansion) and Phase 2 (Monotherapy and Combination).

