Hematology, serum chemistry and coagulation tests will be programmatically graded according to NCI-CTCAE v4.03 toxicity grading as detailed in [Appendix 1 NCI-CTCAE V4.03 Toxicity Grading](#) when applicable. For parameters for which a CTCAE scale does not exist, reference ranges from the local laboratory will be used to determine programmatically if a laboratory parameter is below, within or above the normal range for the subject’s age, sex, etc.

Treatment-emergent laboratory abnormalities will be identified and will be the focus of laboratory data summarization. A treatment-emergent laboratory abnormality is defined as an abnormality that, compared to baseline, worsens by ≥ 1 grade in the period from the first dose of study drug to 30 days after the last dose of study drug. If baseline data are missing, then any graded abnormality (i.e., an abnormality that is Grade ≥ 1 in severity) will be considered treatment-emergent.

For laboratory results entered with inequality symbols ($<$, \leq , $>$, \geq), numeric values will be imputed by ignoring the inequality symbol(s) (e.g. “ <1.71 ” will be imputed as 1.71 for numeric analyses). Imputed values will not be listed in data listings.

For each laboratory test, Baseline and worst (maximum) CTCAE grade post-Baseline will be identified for each subject. For parameters for which a CTCAE scale does not exist, the Baseline and worst post-Baseline value will be identified as being below, within or above the normal range as detailed above. Change from Baseline will be calculated for all post-Baseline results.

Subjects will be characterized only once for a given assay, based on the worst severity grade observed during a period of interest (e.g., during the study or from Baseline to a particular visit).

Hematology, coagulation and serum chemistry data, and changes from Baseline will be summarized by dose level, by visit for visits from Baseline to C2D1 as well as EOT. Urinalysis and pregnancy test results will be listed only. Plasma 4 β -hydroxycholesterol and cholesterol will be listed only.

Shift tables for hematology, coagulation and serum chemistry will also be presented by showing change in CTCAE severity grade from Baseline to worst grade post-Baseline. A shift table for hematology showing change in CTCAE severity grade from Baseline to worst Cycle 1 value will also be presented.

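### Combination Dose Escalation: no blood count is scheduled between Cycle 1 Day 15 and Cycle 2 Day 1, although a Grade 4 count at any time in Cycle 1 is a DLT, and a cohort can be cleared before the Cycle 2 Day 1 count is known

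*Protocol*

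**What the plan says.** **Schedule.** In protocol Table 1 (repeated as SAP Table 2) the haematology row is marked in Cycle 1 for Days 1, 8 and 15. The Day 16 visit exists for Phase 1 subjects, but its haematology cell is empty. The next marked visit is Day 1 of Cycle 2. For the combination parts, footnote 23 limits that visit to 4 days late and none early, because "there must always be at least a full 7-day off treatment recovery period for palbociclib before starting the next 21-day dosing cycle". The notes to Table 1 allow safety laboratory samples one day before a visit.

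**DLT definition.** Section 8.4.2 covers toxicity "which occurs during the DLT evaluation period (Cycle 1) in each cohort". Its haematological items include "Grade 4 neutropenia" and any Grade 4 thrombocytopenia, neither with a minimum duration. A separate item counts a palbociclib delay of more than 7 days in starting Cycle 2.

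**Who counts as assessed.** The DLT-Evaluable Analysis Set (protocol 9.3, SAP 5.4) takes subjects with sufficient dosing who "underwent all treatment and safety procedures through Day 28 or experienced a DLT prior to Day 28". The MTD is determined in this set.

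**When the decision is taken.** Under section 10.1.6 the Safety Review Committee assesses a dose level "after all subjects in the cohort have been followed for at least 28 days after the first dose of ZN-c5". A Cycle 2 Day 1 count is not named as a condition.

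**Reporting.** SAP 6.6.4 states: "A shift table for hematology showing change in CTCAE severity grade from Baseline to worst Cycle 1 value will also be presented". SAP 6.6.1 assigns safety data to nominal visits and lets unscheduled results enter worst-case analyses.

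**The concern.** Observed DLTs are the primary endpoint of the Combination Dose Escalation, and the 3+3 rule turns them directly into the MTD. The plan defines a count-based event over 28 days, but its scheduled counts stop on Day 15. Palbociclib, for which section 2.3.1 lists low blood counts as a known effect, is dosed to Day 21. The next scheduled count is timed to follow the rest week, when a fall in counts may already have recovered.

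A subject with a transient, symptom-free Grade 4 value in that interval has a DLT as the protocol defines it. That subject can nevertheless complete every scheduled procedure and enter the DLT-evaluable set as free of DLT. The error runs one way, because a missed DLT can only help a cohort pass. The committee timing adds to this: a cohort may be cleared before the first count after the gap, or before the Cycle 2 delay item can be judged.

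**Working it through.** **1. Length of the gap (Table 1, its notes and footnote 23)**

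- Nominal: Day 15 to Day 29 = 29 − 15 = 14 days. Days 16 to 28 are 13 days, and 13/28 = 46% of the DLT window.
- Palbociclib is dosed on Days 1 to 21 (section 6.1.2.2). The gap therefore covers 21 − 15 = 6 dosing days and all 7 rest days.
- Shortest with windows: Day 15 visit on Day 17 and the next sample on Day 28 (one day before a Day 29 visit), 28 − 17 = 11 days.
- Longest: Day 15 visit on Day 13 and Cycle 2 Day 1 on Day 33, 33 − 13 = 20 days.

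**2. What the committee can know (sections 10.1.6 and 8.4.2)**

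- 28 days after a Day 1 dose is Day 29.
- The Cycle 2 Day 1 count may come as late as Day 33, so a decision on Day 29 can precede it by up to 33 − 29 = 4 days.
- Cycle 2 is due on Day 29. For a subject who has not started it, a delay of more than 7 days is established only after Day 29 + 7 = Day 36.
- If every subject attends and starts Cycle 2 on Day 29, both facts can be available that day. The text does not make the decision wait for them.

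**3. Effect on cohort clearance**

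The documents give no operating characteristics for the 3+3 rule, so there is no figure to reproduce. Under protocol Table 2 a dose level passes with 0 DLTs in 3 subjects, or 1 in 3 followed by 0 in the next 3:

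P(pass) = (1 − p)³ + 3p(1 − p)² × (1 − p)³

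If a share m of DLTs appears only in the gap and is missed, p is replaced by p(1 − m). Both p and m are assumptions. For p = 1/3 and m = 0, (2/3)³ = 0.296 and 0.444 × 0.296 = 0.132, which sum to 0.428. The MTD criterion, at most 1 DLT in 6, is the corresponding binomial probability.

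| Missed share m | P(pass), true rate 1/3 | P(pass), true rate 40% | P(≤ 1 of 6), true rate 1/3 |
|---|---|---|---|
| 0 | 0.43 | 0.31 | 0.35 |
| 10% | 0.49 | 0.38 | 0.42 |
| 25% | 0.60 | 0.49 | 0.53 |
| 50% | 0.78 | 0.71 | 0.74 |

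**The case against.** The strongest reply is that a reader might infer that low counts after Day 15 go unobserved, and that is too strong. Section 8.2.1.6 allows local laboratory tests for dose adjustment. Section 8.4.3 requires adverse events to be followed until abnormal values resolve, and section 8.4.3.3 holds ZN-c5 for a related Grade 3 or worse event. Febrile neutropenia presents clinically. Suppression that persists should show at Cycle 2 Day 1 or through the delay item. Sections 8.4.3.1 and 8.4.3.2 also defer palbociclib safety handling to prescribing information that cannot be seen here, so further counts may be required there.

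This narrows the point but does not remove it. The follow-up rules act only on an abnormality already known, and the laboratory provision is permissive. Section 8.2.1.6 states eCRF reporting only for local results that lead to a dose change. None of these provisions schedules a count in Days 16 to 28. What remains is the subject without a Grade 3 or worse count on Day 15 who reaches Grade 4 without symptoms and recovers in time.

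A reader might also extend the argument to monotherapy, where one DLT item is "Grade ≥ 3 hematologic toxicity present for more than 7 days". The documents do not support equal force there:

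- A Grade 3 count seen on Day 15 is already known, so sections 8.4.3 and 8.4.3.3 apply.
- A drug-related interruption of 4 days or more is itself a DLT under section 8.4.1.
- The monotherapy Cycle 2 Day 1 window is ± 4 days, so with the one-day allowance the count can fall on Day 29 − 4 − 1 = Day 24.

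On the committee, 28 days after the first dose reaches the nominal Cycle 2 Day 1 date, so in many cohorts the count will be in. The text still permits a decision without it.

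**Conclusion.** The point holds for the Combination Dose Escalation. The count-based DLTs are defined over 28 days but are covered by scheduled counts only to Day 15, and the cohort decision is not tied to the next count. The direction of the error follows from the 3+3 rule: clearance can only become more likely.

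The size is not known. It depends on the share of DLTs confined to the gap, and the documents give neither that share nor the timing of the lowest counts. At a true rate of 1/3 the effect runs from 6 percentage points (43% to 49%, 10% missed) to 35 points (43% to 78%, 50% missed). Nothing in the documents favours the upper end. A reader might infer that the combination MTD or RP2D was set too high; the documents show that this is possible, not that it happened.

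Two questions remain open in the text. It does not say whether a Grade 4 value first found at Cycle 2 Day 1, normally after Day 28, is a Cycle 1 DLT. Nor does it say whether that pre-dose count belongs in the SAP's worst-Cycle-1 table. Nominal visit assignment would label it a Cycle 2 value.

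**What to change.** Reconcile protocol Table 1, sections 8.4.2, 9.3 and 10.1.6, and SAP 5.4 and 6.6.4, leaving the DLT thresholds as they are:

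1. In section 10.1.6, require the Cycle 2 Day 1 pre-dose count and the Cycle 2 start status of every cohort subject before the committee decides.
2. State whether a Grade 4 value at Cycle 2 Day 1 counts as a Cycle 1 DLT, and carry the answer into the DLT-evaluable definition.
3. Include the Cycle 2 Day 1 pre-dose count in the SAP worst-Cycle-1 haematology table, and say so in its title or footnote.
4. Report, by dose level, how many DLT-evaluable subjects had any count in Days 16 to 28, beside the MTD/RP2D result.

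Whether to add a late Cycle 1 count is for the sponsor to decide.

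The cost is a wait of some days per cohort decision: up to 4 days for a count within its window, longer where a Cycle 2 start is delayed. Observed DLT rates may also be slightly higher. No new procedure is needed. SAP section 8 records a data cut-off of 18 May 2022, set after the primary objectives had been met, so item 1 may come too late for cohorts already cleared. Items 2 to 4 can still be applied in the analysis and report.
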